17.6.4 MODIFIED SIMPSON-ANGUS SCALE (SAS)

The SAS is a clinician-rated assessment of neuroleptic-induced Parkinsonism consisting of 10 items. Items are anchor-based, rated on a 5-point scale (ranging between 0 and 4), and address rigidity, gait (bradykinesia), tremor, akathisia, shoulder shaking, glabellar tap, and salivation.

SAS mean score is defined as the average of all 10 items and ranges between 0 and 4. Lower values of the SAS mean score indicate milder symptoms. If one or more of the SAS items are missing at a visit, the SAS mean score will be set to missing for that visit.

The SAS mean score at each visit will be classified as 'abnormal' if it exceeds 0.3 ([Rush, et al., 2000](#)). Otherwise, the non-missing SAS mean score will be classified as 'normal'.

SAS is assessed at these study visits: Visit 2, Visit 3, Visit 5, Visit 10, and Visit 17.

Change from Baseline in SAS mean score at each scheduled visit (Week 1/Visit 3, Week 4/Visit 5, Week 24/Visit 10, Week 52/Visit 17) will be analyzed using an MMRM similar to the model described in [Section 16.1.1.1](#), with Baseline SAS mean score as the covariate. In addition, the MMRM analysis will be performed for subgroups of subjects based on whether the subject took concomitant medications for treatment of movement disorders during the study, which is similar to the model described in [Section 16.1.1.4](#).

Change from Baseline in SAS mean score at each scheduled visit (Week 1/Visit 3, Week 4/Visit 5, Week 24/Visit 10, Week 52/Visit 17) will be analyzed using an ANCOVA model similar to the model described in [Section 16.1.1.3](#) (Analysis of covariance (including LOCF)), with Baseline SAS mean score as the covariate.

The observed SAS mean score and the change from Baseline values will also be summarized

Document: CCI

Author: PPD

Version Number: 0.6

Version Date: 30JAN2023

Template No.: CS_TP_BS016 Revision 6

Reference: CS_WI_BS005

Effective Date: 02Dec2019

descriptively by treatment group and visit. In addition, the observed SAS mean score and the change from Baseline values will be summarized descriptively by the subgroups of concomitant medication use for treatment of movement disorders.

Shift from Baseline in SAS mean score category (Normal/Abnormal) to each post-Baseline scheduled visit (Week 1/Visit 3, Week 4/Visit 5, Week 24/Visit 10, Week 52/Visit 17) and to the overall post-Baseline period (including both the double-blind treatment period and the follow-up period up to and including 9 days after the last dose of study drug) will be summarized descriptively by treatment group.

17.6.5 HEALTHCARE RESOURCE UTILIZATION

Healthcare resource utilization is assessed at these study visits: Visit 2, Visit 7, Visit 10, Visit 13, and Visit 17.

The frequency and percentage of subjects with physician's office visits, ER visits, and hospitalizations (for any reason and those related to schizophrenia) at Baseline and at each post-Baseline scheduled visit (Week 12/Visit 7, Week 24/Visit 10, Week 36/Visit 13, Week 52/Visit 17) (capturing the information during the past 3 months) will be summarized. The number of physician's office visits, ER visits, and hospitalizations (for any reason and those related to schizophrenia) per month at Baseline and at each post-Baseline scheduled visit (Week 12/Visit 7, Week 24/Visit 10, Week 36/Visit 13, Week 52/Visit 17), as well as the average length of hospital stays (for any reason and those related to schizophrenia) at Baseline and at each post-Baseline scheduled visit (Week 12/Visit 7, Week 24/Visit 10, Week 36/Visit 13, Week 52/Visit 17), will be summarized. The frequency and percentage of subjects receiving unpaid care at each time point, along with the average number of hours a caregiver spends per week helping the subject, will also be summarized.

The change in the number of physician's office visits, ER visits, and hospitalizations per month, the average length of hospital stays, and the average number of hours a caregiver spends per week helping the subject from Baseline at each post-Baseline scheduled visit (Week 12/Visit 7, Week 24/Visit 10, Week 36/Visit 13, Week 52/Visit 17) will be summarized.

Shift from Baseline to each post-Baseline scheduled visit (Week 12/Visit 7, Week 24/Visit 10, Week 36/Visit 13, Week 52/Visit 17) in whether the subjects receive unpaid care will also be summarized.

Document: CCI

Author: PPD

Version Number: 0.6

Version Date: 30JAN2023

Template No.: CS_TP_BS016 Revision 6

Reference: CS_WI_BS005

Effective Date: 02Dec2019

18

CCI

19 DATA NOT SUMMARIZED OR PRESENTED

The variables and/or domains not summarized or presented are:

- Subject initials
- Any data collected on screen failures other than disposition, basic demographics, and pre-treatment events.
- Any data collected during previously failed screening(s) for randomized subjects who were screened more than once except Adverse Events.

These domains and/or variables will not be summarized or presented but will be available in the clinical study database and SDTM datasets.

Document:

CCI

Author:

PPD

Version Number:

0.6

Version Date:

30JAN2023

Template No.: CS_TP_BS016 Revision 6

Reference: CS_WI_BS005

Effective Date: 02Dec2019

APPENDIX 1. PROGRAMMING CONVENTIONS FOR OUTPUTS

IQVIA OUTPUT CONVENTIONS

Where applicable, the appendix_compilation_working_Guidelines_ 21Jun2017 Global Final.pdf document – provided by Sunovion – will be followed.

In addition, the following output conventions are to be followed:

- General presentation:
 - The first row in the body of the table or listing should be blank
 - Rounding should be done with the SAS function ROUND.
 - Numbers in tables should be rounded, not truncated.
 - Alphanumeric output should be left aligned.
 - Numbers should be decimal point aligned when possible. When more than 1 statistics is presented per row, alignment on the first value only will be done.
 - Text values should be left aligned.
 - The first letter of a text entry should be capitalized. Title case should be used in headers.
- Univariate Statistics: If the raw data has N decimal places, then the summary statistics should have the following decimal places:
 - Minimum and maximum: N
 - Mean, median, Q1, and Q3: N + 1
 - SD: N + 2
 - For lab data only, in the rare case where raw data has more than 3 decimal places, summary statistics will be presented for the scenario of N = 3. All decimals will be presented in Listings.
 - For UPSM scores, 3 decimal places will be presented for mean, median, Q1, Q3, LS mean, LS

Document: CCI

Author: PPD

Version Number: 0.6

Version Date: 30JAN2023

Template No.: CS_TP_BS016 Revision 6

Reference: CS_WI_BS005

Effective Date: 02Dec2019

mean difference, and 95% CI; 4 decimal places will be presented for SD and SE; 2 decimal places will be presented for min and max. Up to 2 decimal places will be presented in Listings.

- Frequencies and percentages (n and %):
 - Percent values should be reported inside parentheses, with one space between the count (n) and the left parenthesis of the percentage. Parentheses should be justified to accept a maximum of 100.0 as a value and padded with blank space if the percent is less than 100.0.
 - Percentages will be reported to one decimal place, except cases where percent <100.0% but >99.9% will be presented as '>99.9%' (eg, 99.99% is presented as >99.9%); and cases where percent <0.1% will be presented as '<0.1%' (eg, 0.08% is presented as <0.1%). Rounding will be applied after the <0.1% and >99.9% rule.
 - Where counts are zero, no percentage should appear in the output.
- Confidence Intervals:
 - Confidence intervals and estimates are presented to one place more than the raw data, and standard errors to two places more than the raw data.
 - Confidence intervals should be justified so that parentheses displayed on consecutive lines of a table “line up”.
 - Boundary values of confidence intervals should be separated by a comma.
 - Boundary values should be padded as necessary to accept negative values and to allow alignment of the decimal place.
- P-values should be reported to three decimal places, except values <1.000 but >0.999 will be presented as '>0.999' (eg, 0.9998 is presented as >0.999); and values <0.001 will be presented as '<0.001' (eg, 0.0009 is presented as <0.001). Rounding will be applied after the <0.001 and >0.999 rule.
- Ratios should be reported to one more decimal place than the raw data.
- Enough spaces should be left between column to easily distinguish which text pertain to which column.

Document: CCI

Author: PPD

Version Number: 0.6

Version Date: 30JAN2023

Template No.: CS_TP_BS016 Revision 6

Reference: CS_WI_BS005

Effective Date: 02Dec2019

- Missing values:
 - A "0" should be used to indicate a zero frequency.
 - A blank will be used to indicate missing data in an end-of-text table or subject listing.
- Figures:
 - Figures should be provided in RTF files using the SAS Output Delivery System (ODS), as Computer Graphics Metafile (CGM) formatted graphical output generated by SAS.
 - The image should be clear and of high quality when viewed in the Word document, and when printed.
 - In general, boxes around the figures should be used.
- Footers should be defined as follows:
 - Table footnotes should be defined using compute statements in the proc report, and should appear directly after the body of the table.
 - If text wraps across more than one line (for a note), the first letter for all lines of text after the first one will be indented to align beneath the first letter of the text in the first line.

DATES & TIMES

Depending on data available, dates and times will take the form yyyy-mm-ddThh:mm:ss .

SPELLING FORMAT

English US.

PRESENTATION OF TREATMENT GROUPS

For outputs, treatment groups will be represented as follows and in that order:

Document: CCI

Author: PPD

Version Number: 0.6

Version Date: 30JAN2023

Template No.: CS_TP_BS016 Revision 6

Reference: CS_WI_BS005

Effective Date: 02Dec2019

Treatment Group	For Tables (Column Order)	For Listings and Graphs (Order)
SEP-363856 50 to 100 mg/day	SEP-363856 50 to 100 mg/day (1)	SEP-363856 50 to 100 mg/day (1)
Quetiapine XR 400 to 800 mg/day	Quetiapine XR 400 to 800 mg/day (2)	Quetiapine XR 400 to 800 mg/day (2)
	Total (3)	

LISTINGS

All listings will be ordered by the following (unless otherwise indicated in the template):

- Actual treatment group, displaying SEP-363856 50 to 100 mg/day first and then Quetiapine XR 400 to 800 mg/day. Randomized subjects who did not receive any study medication will be presented at the end and labelled “Not Treated”.
- Subject ID
- Visit (where applicable)
- Original date/time (where applicable)

Document:

CCI

Author:

PPD

Version Number:

0.6

Version Date:

30JAN2023

Template No.: CS_TP_BS016 Revision 6

Reference: CS_WI_BS005

Effective Date: 02Dec2019

APPENDIX 2. PARTIAL DATE CONVENTIONS

The actual dates as collected on the CRF will be presented in the listings. Imputed dates will not be presented in the listings unless otherwise specified.

ALGORITHM FOR ADVERSE EVENTS:

As a general rule, if the start date of an AE is available and the start time of the AE is not available, the AE will be considered to have started after the study drug dose administered on the day of the AE start date.

In case of partial or missing AE start and/or end dates, impute partial or missing event start and/or end dates (if not ongoing) using the algorithm below. If an AE has some missing components in both the start and end dates, first impute the end date.

AE end date imputation

- If year and month (YYYY-MM) of AE end date are known, then impute the missing day part to be the last day of the month.
- If only year (YYYY) of AE end date is known, then impute the missing month and day part to be 31st December.

If AE end date is completely missing and AE is not ongoing, then impute AE end date to date of last contact.

AE start date imputation

- If year and month (YYYY-MM) of AE start date are known and YYYY-MM = year and month of 361-304 study med start date, then impute AE start date to the earlier of 361-304 study med start date and AE end date (if non-missing).
- If year and month (YYYY-MM) of AE start date are known and YYYY-MM ≠ year and month of 361-304 study med start date, then impute AE start date to YYYY-MM-01.
- If only year (YYYY) of AE start date is known and YYYY = year of 361-304 study med start date, then impute AE start date to the earlier of 361-304 study med start date and AE end date (if non-missing).

Document: CCI

Author: PPD

Version Number: 0.6

Version Date: 30JAN2023

Template No.: CS_TP_BS016 Revision 6

Reference: CS_WI_BS005

Effective Date: 02Dec2019

- If only year (YYYY) of AE start date is known and YYYY ≠ year of 361-304 study med start date, then impute AE start date to YYYY-01-01.
- If AE start date is completely missing, then impute AE start date to the earlier of 361-304 study med start date and AE end date (if non-missing).

Using the full or imputed event dates, assign events into pre-treatment events vs. AE as described below.

If both event start date/time and 361-304 study med start date/time are available:

- If event start date/time < 361-304 study med start date/time, then pre-treatment event.
- If event start date/time ≥ 361-304 study med start date/time, then AE.

If (event start date is available and time is not available) and/or (361-304 study med start date is available and time is not available):

- If event start date < 361-304 study med start date, then pre-treatment event.
- If event start date ≥ 361-304 study med start date, then AE.

ALGORITHM FOR PRIOR / CONCOMITANT / POST-TREATMENT MEDICATIONS:

The concept of “date” below should also include time information whenever time is available for both comparators.

For the case where the medication start date is known and is equal to SEP-363856/Quetiapine study med end date and the medication start time is unknown, or the case where the imputed medication start date is equal to SEP-363856/Quetiapine study med end date:

- If CRF question ‘Started after last dose of study medication?’ = No, then assign as concomitant.
- If CRF question ‘Started after last dose of study medication?’ = Yes, then assign as post-treatment.

In case of partial or missing medication start or end dates, the following algorithm will be used for determining if a medication is prior, concomitant, or post-treatment. If a medication has some missing components in both the start and end dates, first impute the end date.

Impute stop date as latest possible date:

Document: **CCI**

Author: **PPD**

Version Number: 0.6

Version Date: 30JAN2023

Template No.: CS_TP_BS016 Revision 6

Reference: CS_WI_BS005

Effective Date: 02Dec2019

- If only day unknown, impute as last day of the month.
- If month and day unknown, impute as to the earlier of 31st December and date of last contact.
- If end date is completely unknown and medication is not ongoing, impute to date of last contact.

Impute start date as earliest possible date:

CRF questions: 'Started prior to first dose?' = Yes; 'Started after last dose of study medication?' = No.

- If only day unknown, impute as the later of (first day of the month; date of birth [if full date is available]).
- If month and day unknown, impute as the later (1st January; date of birth [if full date is available]).
- If start date is completely unknown, impute to earlier of (date of informed consent, medication end date [if not missing]).

CRF questions: 'Started prior to first dose?' = No; 'Started after last dose of study medication?' = Yes.

- If only day unknown, impute as the later of (first day of the month; 361-304 study med end date + 1).
- If month and day unknown, impute as the later of (1st January; 361-304 study med end date + 1).
- If start date is completely unknown, impute to 361-304 study med end date + 1.

CRF questions: 'Started prior to first dose?' = No; 'Started after last dose of study medication?' = No.

- If only day unknown, impute as the later of (first day of the month; 361-304 study med start date).
- If month and day unknown, impute as the later of (1st January; 361-304 study med start date).
- If start date is completely unknown, impute to 361-304 study med start date.

Then assign a medication into prior, concomitant, or post-treatment

The concept of "date" below should also include time information whenever time is available for both comparators.

- If medication stop date < 361-304 study med start date, assign as prior.
- If (medication stop date \geq 361-304 study med start date or medication is ongoing) and medication start date \leq 361-304 study med end date, assign as concomitant.
- If medication start date > 361-304 study med end date, assign as post-treatment.

Overriding rule

Document: CCI

Author: PPD

Version Number: 0.6

Version Date: 30JAN2023

Template No.: CS_TP_BS016 Revision 6

Reference: CS_WI_BS005

Effective Date: 02Dec2019

For the case where the medication start date is known and is equal to 361-304 study med end date and the medication start time is unknown, or the case where the imputed medication start date is equal to 361-304 study med end date:

- If CRF question '*Started after last dose of study medication?*' = *No*, then assign as concomitant.
- If CRF question '*Started after last dose of study medication?*' = *Yes*, then assign as post-treatment.

PARTIAL DATE IMPUTATION RULES FOR INITIAL ONSET OF SCHIZOPHRENIA

For subjects with partial onset date of schizophrenia, impute the onset date using the following rules:

- If only day unknown, impute as the earlier of: 15th of the month, or date of ICF.
- If both month and day unknown, impute as the earlier of: June 30th of the year, or date of ICF.

PARTIAL DATE IMPUTATION RULES FOR SCHIZOPHRENIA DIAGNOSIS

For subjects with partial date of schizophrenia diagnosis, impute the date using the following rules:

- If only day unknown and the known year and month is earlier than the year and month of ICF, impute as the later of: 15th of the month, or date of initial onset of schizophrenia (actual or imputed).
- If only day unknown and the known year and month is the same as the year and month of ICF, impute as the later of: earlier of (date of ICF, 15th of the month), or date of initial onset of schizophrenia (actual or imputed).
- If both month and day unknown and the known year is earlier than the year of ICF, impute as the later of: June 30th of the year, or date of initial onset of schizophrenia (actual or imputed).
- If both month and day unknown and the known year is the same as the year of ICF, impute as the later of: earlier of (date of ICF, June 30th of the year), or date of initial onset of schizophrenia (actual or imputed).

PARTIAL DATE IMPUTATION RULES FOR LAST ACUTE EXACERBATION OF SCHIZOPHRENIA

For subjects with partial date of last acute exacerbation of schizophrenia, impute the date using the

Document: CCI

Author: PPD

Version Number: 0.6

Version Date: 30JAN2023

Template No.: CS_TP_BS016 Revision 6

Reference: CS_WI_BS005

Effective Date: 02Dec2019

following rules:

- If only day unknown and the known year and month is earlier than the year and month of ICF, impute as the later of: 15th of the month, or date of initial onset of schizophrenia (actual or imputed).
- If only day unknown and the known year and month is the same as the year and month of ICF, impute as the later of: earlier of (date of ICF, 15th of the month), or date of initial onset of schizophrenia (actual or imputed).
- If both month and day unknown and the known year is earlier than the year of ICF, impute as the later of: June 30th of the year, or date of initial onset of schizophrenia (actual or imputed).
- If both month and day unknown and the known year is the same as the year of ICF, impute as the later of: earlier of (date of ICF, June 30th of the year), or date of initial onset of schizophrenia (actual or imputed).

PARTIAL DATE IMPUTATION RULES FOR FIRST HOSPITALIZATION

For subjects with partial date of first hospitalization for treatment of schizophrenia, impute the date using the following rules:

- If only day unknown, impute as the earlier of: 15th of the month, or date of ICF.
- If both month and day unknown, impute as the earlier of: June 30th of the year, or date of ICF.

PARTIAL DATE IMPUTATION RULES FOR FIRST ANTI-PSYCHOTIC DRUG THERAPY

For subjects with partial start date for the first anti-psychotic drug therapy of at least 2 weeks duration intended for treatment of schizophrenia, impute the start date using the following rules:

- If only day unknown, impute as the earlier of: 15th of the month, or date of ICF.
- If both month and day unknown, impute as the earlier of: June 30th of the year, or date of ICF.

RULES FOR ASSIGNING DOSEON/DOSEA

- In general, DOSEON/DOSEA should be the dose level immediately before the start of an AE or an

Document: CCI

Author: PPD

Version Number: 0.6

Version Date: 30JAN2023

Template No.: CS_TP_BS016 Revision 6

Reference: CS_WI_BS005

Effective Date: 02Dec2019

assessment. In case the AE or the assessment start date/time coincides with the first dosing start date/time of the study, the DOSEON/DOSEA should be assigned to the dose level associated with that first dosing start date/time. In case the AE or the assessment start date/time coincides with a dosing start date/time other than the first dosing start date/time (collected or imputed for Week 1 as specified in Section 14.1), the DOSEON/DOSEA should be assigned to the dose level associated with the previous dosing start date/time.

- In case of missing AE start time, missing assessment (start) time, and/or missing dosing start time, DOSEON/DOSEA should be assigned using the algorithm in the table below.

Scenario	Data	Rules
Dosing start date and start time both available	Adverse Events	If AE start date is available and AE start time is missing, dose on the same day as AE start should be assigned as DOSEON.
	Scales/Questionnaires, Vitals, Labs, ECG	If assessment start date is available and assessment start time is missing, dose on the previous day of the assessment should be assigned as DOSEA.
Dosing start date available but start time missing	Adverse Events	Regardless of whether AE start time is available, dose on the same day as AE start should be assigned as DOSEON.
	Scales/Questionnaires, Vitals, Labs, ECG	Regardless of whether assessment start time is available, dose on the previous day of the assessment should be assigned as DOSEA.

- In case of partial or missing AE start date, the imputed AE start date will be used for the purpose of assigning DOSEON.

Document: CCI

Author: PPD

Version Number: 0.6

Version Date: 30JAN2023

Template No.: CS_TP_BS016 Revision 6

Reference: CS_WI_BS005

Effective Date: 02Dec2019

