At Baseline (Day 1), subjects who have successfully completed the washout of psychotropic medications and have met the eligibility criteria will be randomly assigned via interactive web response system (IWRS) to SEP-363856 or quetiapine XR treatment groups in a 2:1 ratio. Study drug dosing will begin the evening of the Baseline visit. Treatment will continue once-daily, in the evening at bedtime, for the remainder of the Treatment Period, during which the procedures outlined in [Table 2](#) will be conducted. Subjects will be seen at Baseline, Weeks 1, 2 and 4, and then every 4 weeks thereafter up to Week 52. Telephone calls will be made by a member of the clinical research staff to the subjects weekly between visits that are more than one week apart to collect AEs and concomitant medications, as well as to remind subject about adherence to study drug administration and upcoming visits.

Subjects may be hospitalized for the first 7 days of the Treatment Period, if deemed clinically necessary by the Investigator. Further hospitalization during the Treatment Period will require approval from the Medical Monitor.

Subjects randomized to the SEP-363856 group will receive SEP 363856 50 mg/day from Day 1 through Day 3 and 75 mg/day from Day 4 through Day 7. Beginning on Day 8, the dose can be adjusted among 3 dose levels (50, 75 and 100 mg), as deemed clinically appropriate by the Investigator.

Subjects randomized to the quetiapine XR group will receive quetiapine XR 300 mg/day on Days 1 and 2, 400 mg/day on Days 3 and 4, and 600 mg/day from Day 5 through Day 7.

Beginning on Day 8, the dose can be adjusted among 3 dose levels (400, 600, and 800 mg), as deemed clinically appropriate by the Investigator.

Dose adjustments made to either SEP-363856 or quetiapine XR will be done in a blinded fashion.

Dose increases can be made no more frequently than weekly to the next higher dose level beginning on Day 8, if the response to the previous dose level is not adequate and there are no significant tolerability problems, based on Investigator judgement. Increases in dose will occur at regularly scheduled study visits, when possible. However, dose increases between regularly scheduled visits may occur (as long as subject have been taking the previous dose level for at least 7 days). If a dose increase is performed between regularly scheduled visits, subjects will be required to return to the clinic at an unscheduled visit for drug dispensation.

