2.2.4. CCI

3. STUDY DESIGN

3.1. GENERAL DESCRIPTION

This is a 52-week, multicenter, randomized, double-blind, parallel-group, flexible-dose study designed to evaluate the long-term safety and tolerability of SEP-363856 (50 to 100 mg/day) in clinically stable adults with schizophrenia. This study is projected to randomize approximately 300 subjects to two treatment groups (SEP-363856 50 to 100 mg/day or Quetiapine XR 400 to 800 mg/day) in a 2:1 ratio.

Study drug will be taken at the same time each evening at bedtime and should be taken without food or with a light meal.

The study will consist of three periods: Screening/Washout (up to 21 days), Treatment (52 weeks) and a Follow-up Visit (7 days after the last study drug dose).

A study schematic is presented in Figure 1.

Document: CCI

Author: PPD

[figure not shown]
Version Number: 0.6

Version Date: 30JAN2023

Template No.: CS_TP_BS016 Revision 6

Reference: CS_WI_BS005

Effective Date: 02Dec2019

Figure 1: Study schematic

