17.1.1 ALL AEs

All AEs will be summarized by SOC and PT, as well as by SOC, HLT, and PT. The summary by SOC and PT will also be presented for the following subgroups: geographic region, sex, age group, number of prior hospitalizations for treatment of schizophrenia, duration of schizophrenia, and BMI category.

In addition, summary tables (by SOC and PT) will be generated for those AEs starting after the last dose of study drug and those AEs starting more than 1 day after the last dose of study drug.

AEs reported by $\geq 2.0\%$ (without rounding) of subjects in any treatment group will be summarized by SOC and PT.

Non-serious AEs reported by $>5.0\%$ (without rounding) of subjects in any treatment group will be summarized by SOC and PT.

The summary by SOC and PT will be broken down further by maximum severity, by strongest relationship to study medication and by duration of exposure to study medication at earliest onset. These summaries are described in the sections below.

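### Adverse events without a start time are placed after that day's bedtime dose, so dose at onset is probably wrong on dose-change days and last-day events enter the after-last-dose table

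*SAP*

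**What the plan says.** Dosing is in the evening throughout. Protocol 7.1 states: "Study drug dosing will begin the evening of the Baseline visit", and then: "Treatment will continue once-daily, in the evening at bedtime, for the remainder of the Treatment Period". SAP 3.1 agrees: "Study drug will be taken at the same time each evening at bedtime and should be taken without food or with a light meal".

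SAP Appendix 2, in the algorithm for adverse events, sets a general rule for an AE with a known start date and unknown start time: "the AE will be considered to have started after the study drug dose administered on the day of the AE start date".

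The DOSEON/DOSEA rules in the same appendix open with a principle: "In general, DOSEON/DOSEA should be the dose level immediately before the start of an AE or an" assessment. The table below it then says, for AEs: "If AE start date is available and AE start time is missing, dose on the same day as AE start should be assigned as DOSEON". If the dosing start time is missing, the same-day dose is used whether or not the AE has a time. For untimed scales, vital signs, laboratory tests and ECGs the rule runs the other way: "dose on the previous day of the assessment should be assigned as DOSEA".

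SAP 17.1.1 adds: "summary tables (by SOC and PT) will be generated for those AEs starting after the last dose of study drug", together with a second table restricted to AEs starting more than one day after it. Protocol 15.3.6.1 also asks for a separate summary of AEs that start after the last dose, up to nine days.

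**The concern.** The AE rule suits morning dosing. With bedtime dosing, the day's dose comes at the end of the waking day, so an AE dated on a given day will more often than not have begun before that dose.

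Two outputs inherit the error. First, on a day when the dose level changes, DOSEON records a dose that had probably not yet been taken. The error has no fixed direction. On a step up, the AE is given the higher dose. On a day when a daytime AE prompts a reduction that same evening, it is given the lower dose. In a flexible-dose trial that goes to 100 mg/day, above the 75 mg/day multiple-dose maximum tolerated dose reported in Protocol 7.3.2, anyone using DOSEON to look at AEs by dose would want it right. Second, an untimed AE dated on the last dosing day is classed as starting after the last dose, although it probably began on treatment.

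**Working it through.** The plan gives no figure to reproduce, so the check follows the rule through the dosing schedule.

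**1. How often the rule misplaces onset.** The documents give no clock time for the dose, so bedtime B is assumed. If onset is uniform over 24 hours, the share of same-day onsets before the dose is B/24. If onset is uniform over waking hours from 07:00 to midnight (also assumed), it is (B − 7)/17.

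| Assumed bedtime | Whole day | Waking hours |
|---|---|---|
| 20:00 | 20/24 = 83% | 13/17 = 76% |
| 21:00 | 21/24 = 88% | 14/17 = 82% |
| 22:00 | 22/24 = 92% | 15/17 = 88% |
| 23:00 | 23/24 = 96% | 16/17 = 94% |

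The range is about 76% to 96%.

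**2. When DOSEON changes.** Same-day and previous-day doses differ only when dosing starts or the level changes. From the titration in Protocol 10.1.1:

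| Arm | Day | Last dose already taken | Dose assigned by the rule |
|---|---|---|---|
| SEP-363856 | 1 | none | 50 mg |
| SEP-363856 | 4 | 50 mg | 75 mg |
| Quetiapine XR | 1 | none | 300 mg |
| Quetiapine XR | 3 | 300 mg | 400 mg |
| Quetiapine XR | 5 | 400 mg | 600 mg |

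That is 2 of 7 Week 1 days for SEP-363856 and 3 of 7 for quetiapine XR, including Day 1. After Week 1, only adjustment days are affected.

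**3. Timed AEs.** Protocol 10.2 has the time recorded for the first and last administration in each visit period. The step days fall inside the first period. Appendix 2 refers to Week 1 dosing starts as collected or imputed under SAP 14.1, but that section shows no imputed clock time. It follows, as an inference, that an AE timed in the morning of a step day could also be given that evening's dose.

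**4. The last dosing day.** Under the Appendix 2 rule, an untimed AE dated that day follows the final dose and so enters the first table in SAP 17.1.1. It cannot enter the second table, because its start date is the last dosing date itself. For medications in the same position, Appendix 2 uses a CRF question on whether they began after the last dose. The SAP shows no equivalent for AEs.

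**5. What does not move.** SAP 17.1 keeps AEs starting within nine days after the last dose in the main tables, so a last-day AE is counted either way. SAP 17.1.1.3 places AEs after the last dose in the interval of the last day of exposure. On Day 1, SAP 17.1 already counts an untimed event as an AE.

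**The case against.** The strongest reply is that little depends on the rule. Time is used whenever it is available, the number of untimed AEs is unknown, and on most days the two candidate doses are the same. No AE table by DOSEON is visible in the SAP. The second table in SAP 17.1.1 already gives a view of post-treatment AEs without the last-day ambiguity. The assessment rule is also not a perfect model: scheduled assessments take place at visits before a bedtime dose, whereas an AE can start at any hour. Insomnia, among the most common AEs in the extension study described in Protocol 4.2, is a night-time event. All of this stands, and it limits the size of the point. It does not explain why the likelier order of events is reversed, or why the rule departs from the SAP's own principle.

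A reader might infer more than the documents support:

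- **That withdrawal effects are misread.** Neither document says the after-last-dose table is read for withdrawal. Appendix 7 says the sponsor evaluates drug withdrawal through its own SMQ.
- **That AEs which led to stopping are lost or relabelled.** They are identified from CRF fields (SAP 17.1.2 and 17.1.6), whatever their onset time. They enter the after-last-dose table wrongly only if the AE began first and the subject still took that evening's dose.
- **That DOSEON is the only link between AEs and dose.** SAP 17.1.2 to 17.1.5 tabulate AEs by action taken, including dose reduction and increase.
- **That the dose had certainly not been taken.** An AE can start between the bedtime dose and midnight.

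**Conclusion.** The point holds, with limited impact. For an AE dated on a dose-change day after Day 1, the rule probably assigns the wrong DOSEON when the AE has no start time, and may do so for a timed AE when the dosing time is missing. This conflicts with the SAP's principle of using the dose in force just before onset and with its own rule for assessments. An untimed AE on the last dosing day is probably placed wrongly in the table of AEs starting after the last dose.

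The effect is confined to DOSEON in datasets and listings and to that one table. The incidence of AEs, SAEs and AEs leading to discontinuation does not change, nor does the table of AEs starting more than one day after the last dose. The 76% to 96% range rests on assumed clock times and uniform onset. The number of AEs affected cannot be estimated from the documents.

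**What to change.** In SAP Appendix 2:

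- For an untimed AE dated after Day 1, set DOSEON to the previous day's dose.
- Use the same default when the dosing time is missing, unless a recorded AE time clearly falls after bedtime dosing.
- State that an untimed AE dated on the last dosing day is not counted as starting after the last dose.
- Keep the current worst-case rule for Day 1, so that no AE becomes a pre-treatment event.

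The cost is a few lines of text and the reprogramming of one variable and one table. The downside is that a few AEs that truly began between the final bedtime dose and midnight will leave the after-last-dose table. They remain in the main AE tables.
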